[name]
[name]
[contact]
[contact]
E-mail: [contact]

Organization@:

Haukeland Hospital

Investigator:

[name], PhD
Laboratory Medicine and Pathology
Haukeland Hospital
[name]
[name]
[contact]
[contact]
E-mail: [contact]

Organization:

Division of Cancer Prevention, National Cancer Institute

Medical Monitor:

[name]
Lung and Upper Aerodigestive Cancer Research Group
[name]
[name]
[contact]
[contact]
E-mail: [contact]

Scientific Monitor:

[name], MPH
Breast and Gynecologic Cancer Research Group
[name]
[name]
[name]
[contact]
[contact]
E-mail: [contact]

* Protocol Co-Principal Investigator

Site Principal Investigator

@ Biomarker Site; No participant accrual occurs at this site

IND Sponsor: NCI/Division of Cancer Prevention

IND#

IND# 52662

Agent(s)/Supplier:

Exemestane/NCI DCP

NCI Contract #

HHSN26120120034I

Protocol Version Date: February 10, 2018

Protocol Revision or

Amendment #

Version 11, Amendment 3

DCP Protocol Template

-6-

Protocol Template Version 8.3

05/21/2013

SCHEMA

Alternative Dosing of Exemestane in Postmenopausal Women with Stage 0-II ER-Positive Breast Cancer: a Randomized Presurgical Trial

Screening visit (Italian sites only)

For women with prior histopathologic biopsy diagnosis of in-situ or invasive carcinoma without ER assessment, consent to obtain material for ER staining to determining eligibility

For women without a prior histopathologic biopsy, obtain consent to perform core needle biopsy with requisite guidance (palpation or imaging) to assess eligibility criteria based on a diagnosis of ER-positive in-situ or invasive breast carcinoma.

Baseline clinic visit (within 14 days prior to randomization)*

Postmenopausal women with cT₀₋₂, cN₀₋₁, M_x, histologically confirmed ER-positive primary breast cancer or women with larger tumors who refuse neo-adjuvant therapy before surgery. No previous treatment for breast cancer.

Baseline medical history, physical exam, concomitant medication, baseline symptoms, tobacco/alcohol use assessment and blood collection for clinical lab tests and circulating biomarkers

Randomization (day 0)

Eligibility confirmation, randomization (stratification by center and by BMI <25 versus ≥25 kg/m²)

Intervention (N=180)

For at least four up to six weeks

Arm 1: Exemestane 25 mg/daily

Arm 2: Exemestane 25 mg/ 3 times a week (3 active tablets and 4 placebo tablets)

Arm 3: Exemestane 25 mg/once a week (1 active tablet and 6 placebo tablets)

Treatment start (day 1)

The participant starts treatment, a telephone contact will be performed only if different from the randomization day

Telephone contact (a week before surgery +3 days)

Review of self-reported compliance, concomitant medications, toxicity assessment.

Final clinical visit (the day of surgery or the day before)

Physical exam, toxicity assessment, concomitant medications, blood collection for clinical lab tests and circulating biomarkers, compliance/review pill diary. The blood withdrawn for biomarkers will be at 12 hours, 1.5-2.5 days and 5.5-6.5 days from last active dose respectively for arm 1, 2 and 3 depending on scheduled final visit. Participants continue intervention until the night before surgery

Surgery (4 to 6 weeks; ideally at day 29)

Surgery performed; Surgical specimens collected

* After identifying the pool of 180 potentially eligible women with ER-positive in-situ or invasive breast cancer, women in Italy and the U.S. undergo identical procedures. Specifically, consent for blood draw, laboratory testing, completion of questionnaire, etc. -as outlined under baseline clinic visit- will be performed.

Endpoints

Primary endpoint: Percentage change in time of serum estradiol concentration at alternative dosing schedules compared to daily dose.

Secondary endpoints: Safety and toxicity, change in Ki-67 and PgR expression, tissue estradiol, exemestane and 17-dihydroxyexemestane concentration.

Circulating estrogens (including ultrasensitive estradiol measurement), androgens and sex hormone binding globulin, exemestane and 17-dihydroxyexemestane, adipokines, glucose, insulin and lipid profile. Further secondary endpoints will be proteomics and UGT2B17 genotype and measurement of crown-like structures in non-cancerous breast fat tissue.

TABLE OF CONTENTS

COVER PAGE.....	1
SCHEMA.....	7
1. OBJECTIVES.....	10
1.1 Primary Objective.....	10
1.2 Secondary Objectives.....	10
2. BACKGROUND.....	10
2.1 Breast Cancer.....	10
2.2 Exemestane.....	10
2.3 Rationale.....	11
3. SUMMARY OF STUDY PLAN.....	14
4. PARTICIPANT SELECTION.....	15
4.1 Inclusion Criteria.....	15
4.2 Exclusion Criteria.....	15
4.3 Inclusion of Women and Minorities.....	16
4.4 Recruitment and Retention Plan.....	16
5. AGENT ADMINISTRATION.....	16
5.1 Dose Regimen and Dose Groups.....	16

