2.2 Exemestane

Exemestane is an irreversible aromatase inhibitor. This drug is highly specific and inhibits peripheral conversion of androstenedione to estrogen down to 98%. The drug was recently approved for the adjuvant setting, and the placebo-controlled phase III MAP.3 chemoprevention trial showed an overall 65% reduction in breast cancers and a specific ER-positive breast cancer reduction of 73% in the intervention arm compared to the placebo group (3).

Exemestane is in fact a steroidal aromatase inactivator with a long-lasting effect attributable to a tight covalent binding to the enzyme. The estradiol suppression persists for at least 5 days after administration of a single dose (10). This suggests, especially in a prevention setting, the possibility to reduce the dose and change the time schedule, while still maintaining a significant estradiol reduction. A study of 10 patients found that women who took a daily dose of 10 mg of exemestane achieved equivalent estradiol suppression as women who took a dose of 25 mg daily (11).

The exemestane steroidal structure suggests it may have androgenic properties that could potentially counteract any anti-estrogenic properties in bone and possibly sexual function and menopausal symptoms. The favorable profile on bone may represent an advantage of this agent in prevention settings in unaffected women at increased risk for breast cancer.

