5.2 Exemestane Administration

Investigational drug pharmacy will be responsible for drug distribution. [name] (PI) and the local Site Investigators or their designees will be responsible for drug administration. They can delegate to other study investigators (MDs and research nurses) to distribute the agent on their behalf.

Participants will receive a 6-week supply (2 wallets containing 3 blisters each) of the drug/placebo as outlined in the clinical procedure schema (see Section 7.1 for a detailed description). Each wallet will consist of 3 blisters, each blister for 7 days of treatment. Each blister will have 7 tablets numbered from 1 to 7 to clearly mark the order to be taken by the participants. Based on the arm, the blister will contain 7 active tablets 1 through 7, or three active tablets corresponding to days 1, 3 and 5 and four placebo tablets at days 2, 4, 6 and 7, or one active tablet placed at day 1 and 6 placebo in the remaining 6 days. The participant will be advised to take one tablet per day after dinner, always at approximately 8 PM, starting from day 1 till the night before surgery. If for any reason they will skip a tablet they will be instructed to leave it behind and take the one for the corresponding day. Participants will be asked to contact the study coordinator the first time they miss a dose.

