7. CLINICAL EVALUATIONS AND PROCEDURES

7.1 Schedule of Events

The possibility of taking part in a pre-surgical trial will be presented to incoming postmenopausal women with a highly suspicious palpable lesion or a newly diagnosed ER-positive DCIS or breast cancer. The baseline visit will be scheduled for interested potential participants after histological confirmation.

SCHEDULE OF EVENTS

Evaluation/ Procedure	Screening Visit ¹	Baseline Visit/ Registration (within 14 days prior to randomization)	Randomization	Phone call (Day 1)	Phone call (1 week +3 days prior to surgery) ²	Final Visit (Days 28+1, 35+1, or 42+1) ³	Surgery (Days 29, 36 or 43) ¹²
Screening Informed Consent	X						
Tru-cut biopsy (Eligibility ER + breast cancer)	X						
Informed Consent		X					
Assess eligibility		X					
Medical history		X					
Physical exam/ height/weight/vital signs		X				X ^{9,10}	
Tobacco / alcohol use assessment		X					
Fasting blood lab tests ⁴		X				X	
Blood lab tests that may not be fasting ⁵		X				X ¹⁰	
Fasting blood for biomarkers ⁶		X				X	
Tissue for biomarkers (FFPE blocks or slides)		X					X
Frozen tissue for biomarkers							X
Frozen tissue for proteomics ¹¹							X ¹¹
Concomitant medications		X			X	X	
Baseline symptoms		X					
Confirm eligibility		(X)	X				
Randomization			X				
Dispense study agent ¹³			X ¹³				
Treatment initiation				X ⁷			
Collect study agent						X	X
Compliance					X	X	
Review agent diary/record						X	
Adverse events					X	X	
QoL questionnaire ⁸		X				X	

¹ For the Italian sites only

² If the participant is seen on site for the physical exam and blood safety tests on Day 7 prior to surgery, perform all procedures in person rather than as a phone call. In all other cases call the participant on the phone 1 week +3 days prior to surgery

³ Based on institutional procedure, the final visit may occur on the same day as surgery or the day before. The Final Visit must be

conducted on Days 28+1, 35+1, or 42+1.

⁴ **Fasting** blood lab tests (local lab): Glucose, total cholesterol, HDL cholesterol and triglycerides. Fasting is strongly recommended, but is not mandated. Every effort should be taken to draw these labs fasting.

⁵ Blood tests for safety that do not require fasting: complete blood count (CBC), AST, ALT, Na, K, BUN, total bilirubin, Cl, Ca, alkaline phosphatase, creatinine, and FSH if needed

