7.3 Baseline Testing/Pre-study Evaluation

Pre-study evaluation is:

- ER positive (ER \geq 10%) breast cancer histologically confirmed

Baseline exams are:

- **Fasting** blood lab tests that are performed at the local lab (glucose, total cholesterol, HDL cholesterol and triglycerides). Fasting is strongly recommended, but is not mandated. Every effort should be taken to draw these labs fasting.
- Blood lab tests for safety that do not require fasting (complete blood count (CBC), AST, ALT, Na, K, BUN, total bilirubin, Cl, Ca, alkaline phosphatase, creatinine, and FSH if needed)
- Fasting blood sample collection for biomarkers. Fasting is strongly recommended, but is not mandated. Every effort should be taken to draw these labs fasting.

- Physical exam and medical history, vital signs, alcohol and tobacco assessment, anthropometric measurement (height, weight, waist measurement, hip measurement) and quality of life assessment; for the purpose of the present study, minimal requirement for the physical exam visit include the following body/system sites: breasts/ cardiovascular/ gastrointestinal/ lymphnodes

For any participant who is deemed as screen failure, blood samples collected at Baseline are to be destroyed locally at the respective Participating Organization (PO). A Note to File detailing the destruction procedure and associated information is to be generated and documented in the participant's research folder or electronic health record.

At the baseline clinic visit, participants will be instructed on the importance of drug compliance. Participants will be provided and instructed on the use of a pill diary to be completed daily, signed and dated by the participant. Participants will be informed that a pill count will be conducted on their study medication use so that their study medication blisters with remaining tablets must accompany them to the subsequent clinic visit.

Plan the beginning of drug administration according to the day fixed for surgery. Surgery must occur on Days 29, 36 or 43. For this study coordinators are advised to count back from the day of surgery so that participants can either have 28, 35 or 42 days of study agent (ending on the 7th day of blister pack). Study agent can be dispensed in advance of starting agent on Day 1, However, coordinators must remind the participants not to start the study agent until a specific day set for the start of study drug.

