7.5 Evaluation at Completion of Study Intervention

At the final visit, participants will undergo physical exam, vital signs, and anthropometric measurements (weight, waist measurement, hip measurement). These procedures may be done **within 7 days prior to surgery or on the day of surgery**. Do not repeat the height assessment at the Final Visit. Height measurement will be used from the baseline visit.

Blood tests for safety that do not require fasting may be done **within 7 days prior to surgery or on the day of surgery**:

- complete blood count (CBC), AST, ALT, Na, K, BUN, total bilirubin, Cl, Ca, alkaline phosphatase, and creatinine

All other procedures are performed the day of surgery or the day before surgery:

Fasting blood lab tests that are performed at the local lab (glucose, total cholesterol, HDL cholesterol and triglycerides). Fasting is strongly recommended, but is not mandated. Every effort should be taken to draw these labs fasting.

Fasting blood for biomarkers will be collected. Fasting is strongly recommended, but is not mandated. Every effort should be taken to draw these labs fasting.

The date and time of blood draw, the date and time of surgery, and the date and time of last pill intake will be recorded.

The use of concomitant medications, adverse events, compliance, and quality of life assessment will be assessed. Study agent will be collected. A review of agent diary will be performed.

Any kind of surgery will be allowed from simple lumpectomy to total mastectomy. Tissue samples will be collected from the surgical specimen and processed according to Section 10. A detailed Manual of Operations and Procedures will be implemented with the specific procedures for each specimen.

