10.2.1 Blood

It is strongly recommended for all blood samples for biomarkers to be drawn under fasting condition (at least 6 hours) preferably between 8 a.m. and 10 a.m. at baseline and the day of surgery (or the day before, depending on the local institutional procedures).

A total of **10 ml of blood** will be withdrawn for **safety lab exams and lipid profile** at baseline and before surgery.

At baseline and before surgery a total of **20 ml of blood** will be collected into vacuum blood collection tubes containing beads coated with clotting activator for **serum** separation to be employed for circulating **biomarker analysis**. Accordingly with specific tubes adopted at your hospital, please refer to the manufacture instructions. Allow the blood to clot at room temperature for 30 minutes. Then, spin in centrifuge for 10 minutes. Sarstedt Serum Monovettes tubes require 10 min centrifugation at 2000 x g at room temperature, while BD Vacutainer® SST™ and PST™ gel tubes should be spun at a speed of 1300 x g. Swing-out buckets best option for both systems. . After centrifugation, the yellow top layer, which corresponds to serum, is pipetted using the disposable transfer pipettes in 10 even aliquots (about 1.0 mL each) into the polypropylene cryotubes (Thermo Fisher Scientific), specifically labeled according to the Instructions in the Manual of Operations and Procedures. Tubes are tightly capped and stored in a dedicated – 80°C freezer equipped with a temperature control and temperature log chart or an alarm monitoring system per institutional standards.

At baseline and before surgery a total **3 ml whole blood** will be collected in tubes containing EDTA-K2 as anti-coagulant agent. The tube is gently mixed and blood is pipetted using disposable transfer pipettes in 2 even aliquots (about 1.5 mL each) into the polypropylene cryotubes (Thermo Fisher Scientific), specifically labeled according to the Instructions in the Manual of Operations and Procedures . Tubes are tightly capped and stored in a dedicated –80°C freezer equipped with a temperature control and

temperature log chart or an alarm monitoring system per institutional standards.

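### Letting sites draw the primary-endpoint serum the day before surgery shortens time since last active dose by 24 hours in the weekly arm and not at all in the daily arm, and may favour weekly non-inferiority.

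*Combined protocol and SAP*

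**What the plan says.** **Draw day.** Section 7.1, footnote 3: "Based on institutional procedure, the final visit may occur on the same day as surgery or the day before". Section 7.5 lets the safety bloods and physical exam be done up to a week early, then fixes the rest, including biomarker blood: "All other procedures are performed the day of surgery or the day before surgery". The Schema gives the resulting times since the last active tablet: "at 12 hours, 1.5-2.5 days and 5.5-6.5 days from last active dose respectively for arm 1, 2 and 3 depending on scheduled final visit".

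**Clock.** Section 5.2: "The participant will be advised to take one tablet per day after dinner, always at approximately 8 PM". Section 10.2.1 prefers a morning draw: "preferably between 8 a.m. and 10 a.m. at baseline and the day of surgery", or the day before according to local procedure. Section 7.3: "Surgery must occur on Days 29, 36 or 43", with coordinators counting back so that dosing ends on the seventh day of a blister.

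**Active tablets.** In the three-times-weekly arm, Section 5.2 specifies "three active tablets corresponding to days 1, 3 and 5 and four placebo tablets at days 2, 4, 6 and 7". In the weekly arm only the day 1 tablet of each blister is active.

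**Evidence on duration.** Section 2.2: "The estradiol suppression persists for at least 5 days after administration of a single dose". No figure is given for days 5 to 7.

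**Analysis.** Section 13.4 sets a 6-point margin, SD 11, one-sided alpha 0.025 and 54 evaluable women per arm. It names time since last dose among the possible ANCOVA confounders. Section 13.2 stratifies by center. Section 7.5 records the times of the draw, of surgery and of the last pill.

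**The concern.** The trial asks whether one tablet a week suppresses estradiol about as well as one a day. For the weekly arm the open part of that question is the end of the interval, beyond the five days that the protocol can support. A 6.5-day draw looks a day and a half into that stretch; a 5.5-day draw looks half a day into it. The daily arm is sampled at the same 12 hours whichever day is chosen, so the choice moves one side of the weekly-versus-daily comparison and leaves the other fixed.

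Estradiol can only stay level or rise as the last active dose recedes, so any resulting error in the weekly comparison runs towards non-inferiority. The pooled estimate would also depend on how much each site recruits and which day it uses, and the endpoint definition in Sections 8.1 and 13.4 does not state a sampling time.

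**Working it through.** **1. The plan's own figures.** With margin 6, SD 11, true difference 0 and one-sided alpha 0.025, the non-central t gives 79.4% power at 53 per arm and 80.2% at 54. The planned 54 reproduces, and 162 / 0.90 = 180 randomized.

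**2. The draw windows.** Take 28 days of treatment, tablets at 8 PM and a draw at 8 AM. The last active tablet in the three-times-weekly arm is on day 26 and in the weekly arm on day 22. The next active tablet in each would fall on day 29.

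| Arm | Since last active dose, day before (day 28) | Since last active dose, day of surgery (day 29) | Left before next active dose, day before / day of |
|---|---|---|---|
| Daily | 0.5 d | 0.5 d | 12 h / 12 h |
| Three times weekly | 1.5 d | 2.5 d | 36 h / 12 h |
| Weekly | 5.5 d | 6.5 d | 36 h / 12 h |

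This matches the Schema; 35 and 42 days of treatment give the same intervals. The day-of-surgery draw is itself 12 h short in every arm, so the day-before option accounts for 36 − 12 = 24 h.

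**3. Size of a possible bias in the weekly arm.** The documents give no recovery rate. Assume r percentage points of baseline estradiol regained per day between the two possible draws. If a fraction f of draws is the day before, the weekly deficit is understated by f × r points. The standard error of the arm difference is 11 × √(2/54) = 2.12 points. Set the true deficit on a day-of-surgery draw at exactly 6, so that declaring non-inferiority is an error with nominal probability 2.5%. The actual probability is the upper tail of the non-central t on 106 degrees of freedom, with non-centrality f × r / 2.12:

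| r (assumed) | all draws day before (f = 1) | half day before (f = 0.5) |
|---|---|---|
| 0 | 2.5% | 2.5% |
| 0.5 | 4.2% | 3.3% |
| 1 | 6.8% | 4.2% |
| 2 | 15.3% | 6.8% |
| 3 | 28.9% | 10.4% |

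The documents do not give f either.

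**4. Does the listed covariate repair it?** Assume half of each arm is drawn on each day. Mean times since last active dose are 0.5, 2 and 6 days. The within-arm variance is 0, 0.25 and 0.25, averaging 0.167. The total variance is 5.556. Arm therefore explains 1 − 0.167/5.556 = 97% of the covariate (variance inflation 33). The adjusted variance of weekly minus daily is 121 × [2/54 + 5.5² / (162 × 0.167)] = 121 × 1.157 = 140, so the SE rises from 2.1 to 11.8 points and power falls from about 81% (normal approximation) to 7%. For three times weekly minus daily, 121 × [2/54 + 1.5²/27] = 14.6, so the SE is 3.8 and power about 35%. Adjustment would also compare arms at an equal time since dose, which is not the comparison of schedules.

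The recorded last pill does not supply the covariate directly either: before the final draw it is a placebo tablet in both sparse arms. Time since last active dose has to be derived from the blister day.

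**5. Does stratification repair it?** Stratifying by center should roughly balance draw day across arms. It does not remove an effect that balanced draw days produce in one arm and not in another.

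**The case against.** **No recovery rate is documented.** The five days in Section 2.2 are a lower bound after a single dose, not a time at which recovery begins. This stands: the bias may be zero.

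**The three-times-weekly arm.** A reader might infer that both sparse schedules are flattered. At 1.5 or 2.5 days that arm is inside the documented period on either draw day, so the documents do not support it.

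**36 hours.** A reader might charge the whole unobserved tail to the day-before option. Of the 36 h, 12 h remain with a day-of-surgery draw; the option costs 24 h.

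**Lower success rates are not all prevented errors.** If the deficit starts from nothing at day 5 and grows linearly, it reaches 6 points at 6.5 days only at 6/1.5 = 4 points per day. At 3 points per day it is 4.5 points at 6.5 days, still inside the margin. The chance of declaring non-inferiority would fall from 56% on day-before draws (deficit 1.5) to 10% on day-of-surgery draws, but a reader should not take that fall as error prevented. The table above therefore fixes the day-of-surgery deficit at the margin instead, which for r below 4 means that part of the deficit is already present by day 5.

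**Detection limit.** Section 13.4 expects many final values below the limit, and Section 9.1 assigns them half of 2 pg/ml. Recovery below the limit would then not show on either day, so a linear shift with constant SD may overstate the effect. This stands in part; Section 13.6 also considers estimating such values.

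**The target.** The protocol never says that the endpoint refers to the end of the interval. Averaged over a week, time since active dose is 3.5 days in the weekly arm, so even a 5.5-day draw is later than average. That is fair, but counting back so that dosing ends on blister day 7 makes an end-of-interval reading the natural one, and no sampling time is stated for any other target.

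**Conclusion.** The point holds for the weekly arm, as a possible bias that can run only towards non-inferiority. The day-before option is explicit, and it shortens time since last active dose from 6.5 to 5.5 days in that arm while leaving the daily arm at 12 hours. Neither center stratification nor the listed covariate removes the consequence.

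The size cannot be had from the documents. The figures of 6.8% and 15.3% rest on assumed recovery of 1 and 2 points per day, a true day-of-surgery deficit exactly at the margin, every draw on the day before, SD 11 and a linear scale. With half the draws on the day before they are 4.2% and 6.8%; with no recovery the rate stays at 2.5%. It would go too far to say that the plan is shown to flatter the weekly schedule. The sample size is not in question.

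**What to change.** Make the morning of surgery the standard time for the biomarker serum at every site. It is already permitted, so the change is amendment wording in the Schema and Sections 7.1, 7.5 and 10.2.1. No dosing changes, and the rest of the final visit can stay as it is.

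Where a site cannot comply:
- record the draw day, and derive time since last active dose from the blister day;
- keep all randomized women in the primary analysis;
- prespecify weekly against daily by draw day as a sensitivity analysis;
- state the sampling time beside any claim of weekly non-inferiority.

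Do not rest the conclusion on the 6.5-day draws alone. Section 13.8 bars sub-analyses as the basis for efficacy conclusions. If half the draws qualified (27 per arm, an assumption), the SE would be 11 × √(2/27) = 2.99 points and power about 50%.

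The cost is a one-day shift of the draw at some sites, whose burden the documents do not let one judge, and a sensitivity analysis with low power. If there is no recovery after day 5, the change leaves the expected result as it was.
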